10.5. Sample size

The purpose of the study is to assess the durability and performance of the TIES® Port over one year. The table below shows the power to demonstrate non-inferiority to within 10% of the target 24-week performance criterion of 70% of subjects with the device *in situ* experiencing no leakage (i.e. lower two-sided 95% confidence limit no less than 60%) according to the true proportion and number of assessable subjects.

True proportion experiencing no leakage at 24 weeks	200 subjects	180 subjects	160 subjects	140 subjects	120 subjects
70%	87%	83%	79%	73%	67%
71%	93%	90%	87%	82%	76%
72%	97%	95%	92%	89%	83%
73%	99%	98%	96%	93%	89%
74%	99%	99%	98%	97%	94%
75%	100%	100%	99%	98%	97%

CLINICAL INVESTIGATION PLAN

There will be sufficient power with the planned 200 subjects to demonstrate non-inferiority of the TIES® Port with respect to the primary performance criterion (efficacy when device used as intended), if at least 80% of subjects are evaluable at 24 weeks (i.e. with at least 160 subjects). If the true proportion of patients experiencing no leakage is higher than the expected minimum of 70% there will be sufficient power to demonstrate non-inferiority even with fewer than the expected proportion of evaluable subjects at 24 weeks.

10.6. Durability Evaluation

Durability of use is evaluated by the cumulative proportion of subjects with the TIES® Port *in situ* at each of the following timepoints of 8, 16, 24, 36 and 52 weeks. These are secondary endpoints.

Durability will be computed by lifetable methods as the complement of the cumulative proportion of subjects in whom the TIES® Port has been removed or has spontaneously explanted, with subjects censored if they withdraw from the study with the device *in situ*, have insufficient follow-up time, or the device is removed for reasons unrelated to device performance.

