4. STUDY OBJECTIVE AND ENDPOINTS

The primary objective is to evaluate the safety, performance and durability of the TIES® Port to 52 weeks in subjects after implantation. The secondary objective is to evaluate Quality of Life (QoL) in subjects implanted with the TIES® Port.

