5.3.4. Withdrawal

Early termination of study participation will be documented for patients that have signed an informed consent form and who exited for any of the following reasons:

- Subject for whom the implantation procedure has been attempted but cannot completed, for example, due to technical reasons. (These subjects will be followed for six months.)
- Subject who are explanted. (These subjects will be followed for six months.)
- Subject no longer wishes to continue with the study follow-up. No further follow up applies.
- Investigator believes it is the best medical interest of the subject to discontinue study participation due to safety reasons. (These subjects will be followed until study procedure related adverse events have resolved.)
- Death of the subject.

No additional subjects will be recruited to compensate for subjects who withdraw or are withdrawn from the study.

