6.11. Follow-up treatment after end of investigation

The investigation sponsor will provide explantation of the device during the clinical investigation if necessary (see Explantation procedure, below). At the end of the investigation, subjects have the right to choose whether to retain the device or to have the device removed. The same applies should the investigation be temporarily halted, or early terminated. The decision will be made in accordance with the investigator and based on

CLINICAL INVESTIGATION PLAN

investigator judgement. If the subject keeps the device in place, the subject will be followed up by his/her general stoma team per standard stoma care and standard care for a non CE-marked device outside the investigation.

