6.16.2. Explant Procedure (if applicable)

If the TIES® Port must be removed, it can be done using standard surgical procedures.

Should there be a reason for explanting the implant and/or the surrounding tissue, it shall be removed in a manner that causes minimal damage to both the implant and the tissues. It is particularly important that implant surfaces and adjacent tissues are kept intact.

See the Surgical Procedure Manual (Appendix) for further detail.

Information on the explant procedure must be documented in source notes and captured in the Case Report Form on "Explant procedure".

All explanted devices must be immediately put into neutral buffered 10% formalin for tissue fixation and returned to the sponsor OstomyCure for evaluation.

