10.7. Safety Evaluation

Safety outcome measures are secondary endpoints and will be analysed as proportion of all implanted subjects using descriptive statistics. Safety information will be collected during the following intervals: during hospitalisation, interval from discharge to 4-weeks visit, interval after the 4-weeks visit including 8-weeks visit, interval after the 8-weeks visit including 16-weeks visit, interval after the 16-weeks visit including 24-weeks visit, interval after the 24-weeks visit including 36-weeks visit, and interval after the 36-weeks visit including 52-weeks visit.

Secondary endpoints are:

- Proportion of implanted subjects with treatment emergent adverse events. Treatment emergent adverse events are defined as events with onset during or after the implantation procedure.
- Proportion of implanted subjects with peristomal skin lesions will be evaluated using a validated 5-point scale by assessing signs of erythema, erosion, or papular lesions.
- Proportion of implanted subjects with device-related adverse event.
- Proportion of implanted subjects with device displacement, device revision or device replacement.

Photographs of the stoma are to be taken to document the ingrowth into the TIES® Port, surrounding peristomal skin and position of the implant at 4, 8, 16, 24, 36 and 52 weeks after implantation. At least 4 views are to be taken: horizontal, vertical frontal, vertical right and vertical left. Additional views may be required if skin lesions or device displacement develop.

The adverse events complicating end-ileostomy, continent ileostomy and pelvic pouch are well described in the literature. Adverse events known to complicate end-ileostomy include peristomal skin problems, infection, abscess, entero-cutaneous fistula, necrosis, stenosis, prolapse, retraction, parastomal hernia, incisional hernia, obstruction to emptying of intestinal contents. That said, the exact incidences are unknown because many reports are retrospective and the experience of the site may influence the outcomes.

All adverse events, device-related complications and device deficiencies or malfunctions described in section 4 will be fully summarized. Adverse events are to be assessed for seriousness and causality.

CLINICAL INVESTIGATION PLAN

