10.9. Statistical analysis

Statistical analyses will be done using SAS System®, Version 9.2 or further and a complete statistical analysis plan will be written before the conduct of analysis. All statistical analyses will be made on locked databases following data clarifications resolved due to Data Management process.

No replacement of missing data is planned in the statistical analysis.

No statistical testing will be conducted for any other parameters in the study and only descriptive analysis will be provided to fully describe the parameters recorded.

Continuous variables will be summarized using standard quantitative statistics: number of non-missing observations, mean, standard deviation, median, quartiles and range (minimum and maximum observed values). The number of missing observations will also be specified.

Categorical variables will be summarized using classical frequency statistics: number of non-missing observations and percentages by categories. Percentages will be calculated on the number of non-missing observations. The number of missing observations will also be specified.

Durability of use will be analysed using lifetable methods to allow for censoring due to subject withdrawal and device removals for reasons unrelated to device performance.

Two-sided 95% confidence intervals will be computed for all primary and secondary endpoints.

A statistical analysis plan will be written to describe all derived variables used in the reporting (especially for all parameters to be compared in time: EQ-5d and Montreux QoL questionnaire) and the statistical tables and listings to be generated.

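### Durability is named as the proportion of subjects with the Port in situ, but the planned life table estimates freedom from performance-related removal, and no named endpoint reports removal from all causes

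*Combined protocol and SAP*

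**What the plan says.** Section 10.6 opens with the quantity: "Durability of use is evaluated by the cumulative proportion of subjects with the TIES® Port" in situ at 8, 16, 24, 36 and 52 weeks, as secondary endpoints. The next sentence gives the computation. It is a life table taking one minus the cumulative proportion whose Port was removed or came out spontaneously, with censoring at withdrawal with the device in place, at insufficient follow-up, "or the device is removed for reasons unrelated to device performance". The synopsis and section 4.2 use the same two sentences. Section 10.9 repeats that life-table methods are used "to allow for censoring due to subject withdrawal and device removals for reasons unrelated to device performance".

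The nearest other endpoint, in section 10.7, is "Proportion of implanted subjects with device displacement, device revision or device replacement". Removal is not in that list.

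The data on removals are collected. Section 6.16.2 states: "Information on the explant procedure must be documented in source notes and captured in the Case Report Form". Section 5.3.4 lists explanted subjects as a documented category of early termination: "Subject who are explanted. (These subjects will be followed for six months".

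The synopsis and section 6.9 allow a second implant. Section 10.6 makes no exception for a Port that is removed and then replaced.

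**The concern.** A subject whose Port was taken out for a reason judged unrelated to performance has no Port in situ, yet that removal never lowers the durability figure. The subject leaves the risk set as if still able to contribute a later performance-related removal. The definition and the computation therefore describe two different quantities.

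Durability belongs to the main aim of the study. Section 4 says: "The primary objective is to evaluate the safety, performance and durability of the TIES® Port to 52 weeks". Section 10.5 also names it in the purpose of the study. The primary performance endpoint is assessed only among subjects with the Port in place, so the share who still have one is what a reader needs in order to relate the 70% criterion to everyone implanted.

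Unrelated removals are foreseeable. Section 1.5 reports Ports explanted during hernia repair in the earlier studies. Section 7.1.2 lists hernia among the risks of implantation, while section 7.1.7 considers the implant unlikely to change its occurrence. The same explant could thus be classed either way, and the plan gives no criteria for unrelated and does not say who decides.

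**Working it through.** **The plan's own figures.** The plan states no durability target, rate or precision, so there is no durability figure to reproduce. Its only computed figures are the power table in section 10.5. With 70% true success and 200 subjects, Φ(0.10/√(0.7 × 0.3/200) − 1.96) = 87.0%, against 87% stated. All 30 cells reproduce in this way. Durability does not enter that calculation.

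**Inputs.** From the plan: n = 200 (the minimum enrolment, taken here as all implanted) and intervals 0–8, 8–16, 16–24, 24–36 and 36–52 weeks. Assumed: D = 20 performance-related removals by week 52, C unrelated removals, no other censoring, and at first no replacement.

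**Formulas.** Planned estimate: S = Π[1 − d_j/(n_j − c_j/2)], with n_(j+1) = n_j − d_j − c_j. In-situ proportion: (200 − D − C)/200.

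**One case in full.** Take D = 20 and C = 10, that is 4 and 2 per interval. The effective numbers at risk are 199, 193, 187, 181 and 175. S = 0.97990 × 0.97927 × 0.97861 × 0.97790 × 0.97714 = 0.897. In situ: 170/200 = 85.0%. The gap is 4.7 points.

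**Range, removals spread evenly over time, D = 20.**

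| Unrelated removals | Planned estimate, week 52 | In situ, week 52 | Gap, week 52 | Gap, week 24 |
|---|---|---|---|---|
| 0 | 90.0% | 90.0% | 0 | 0 |
| 2 (1%) | 89.9% | 89.0% | 0.9 | 0.5 |
| 4 (2%) | 89.9% | 88.0% | 1.9 | 0.9 |
| 10 (5%) | 89.7% | 85.0% | 4.7 | 2.3 |
| 20 (10%) | 89.4% | 80.0% | 9.4 | 4.5 |

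**Sensitivity to the related rate.** Let p and u be the week-52 proportions with related and unrelated removal. With proportional hazards the planned estimate is (1 − p − u)^(p/(p+u)). For u = 2%, the gap is 1.9 points at p = 5% (94.9% against 93.0%), 1.9 at p = 10%, and 1.8 at p = 20% (79.8% against 78.0%). The gap is close to the unrelated share itself.

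**Replacement.** Take D = 20 and C = 2, for which the planned estimate is 89.95%. Suppose r of the 20 related removals are followed by a second Port that stays in. Then (178 + r)/200 have a Port: 89.5% for r = 1, 90.0% for r = 2 and 90.5% for r = 3. From r = 2 on, the planned estimate is the lower of the two; at r = 3 it is lower by 0.55 points.

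**The case against.** The strongest reply is that the rule is open and consistent. The computation stands directly after the definition in three places and is repeated in section 10.9, so the two sentences can be read as one operational definition. Cause-specific retention is a recognised quantity. This stands as far as it goes: nothing is hidden and the method is not invalid. But disclosure does not turn the computed quantity into the named one.

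Second, a reader might infer that the planned figure always overstates the share with a Port. The documents do not support that. Second implants are allowed, a replaced Port counts as removed, and section 1.3 records 13 implantations in 11 patients in the earlier studies. The direction holds only with replacement left aside.

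Third, all-cause removal could be pieced together from the explant form, the exit categories, or the denominators of the quality-of-life summaries. That is true of the data, so a reader who infers that the information is lost would be wrong. It is still not a durability estimate at the five timepoints.

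Fourth, the size is hypothetical. At 1–2% unrelated removals the gap of 0.9–1.9 points lies inside the 95% half-width at 90% with 200 subjects, 1.96 × √(0.9 × 0.1/200) = 4.2 points. The 9.4-point case needs as many unrelated as related removals, and exclusion criterion 1 now bars concurrent hernia. This limits the urgency. A labelling mismatch is not sampling error, however, and a confidence interval does not cover it.

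**Conclusion.** The point holds in this form. The named quantity and the computed quantity differ, and no named endpoint supplies the all-cause figure. With replacement left aside, the planned estimate exceeds the in-situ proportion whenever any removal is classed as unrelated, by about the unrelated share; with none so classed, the two are equal. Once replacement is allowed for, the net direction depends on counts that the documents do not give. Every removal and replacement count used here is an assumption.

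A reader might go further and infer that the study's success criterion is compromised. It is not: durability is secondary and descriptive, has no threshold, and does not enter the 24-week test. The correction is worth making because durability is part of the primary objective and the full SAP is still to be written.

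**What to change.** In the synopsis and sections 4.2, 10.6 and 10.9:

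- Report as durability a life table at 8, 16, 24, 36 and 52 weeks. Every removal of the originally implanted Port, for any cause and whether or not it is replaced, and every spontaneous explantation is an event. Censor at withdrawal, death or end of follow-up with that Port in situ. Time runs from the first implantation, since section 6.9 restarts the visit schedule after a second implant.
- Beside it, give the number of subjects whose Port was replaced and who have a Port in situ at each timepoint. In the replacement example with r = 3, this reads 178/200 = 89.0% with the original Port and 3 more with a replacement, 181/200 = 90.5% in all.
- Keep the planned analysis as a companion labelled freedom from performance-related removal or spontaneous explantation. Fix the qualifying causes in the SAP before data are seen.

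Censoring at death should matter little. With 24 removals and 4 deaths among 200 (assumed), it gives 87.87%, against 88.00% with death as a competing event. Report the number of deaths. Section 6.11 lets subjects choose removal at the end of the study and adds: "The same applies should the investigation be temporarily halted, or early terminated". The SAP should say whether follow-up for this analysis ends at such a date.

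The cost is wording and one extra standard analysis from data already collected. The headline retention figure will be equal to or somewhat lower than the planned one.

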10.7. Safety Evaluation

Safety outcome measures are secondary endpoints and will be analysed as proportion of all implanted subjects using descriptive statistics. Safety information will be collected during the following intervals: during hospitalisation, interval from discharge to 4-weeks visit, interval after the 4-weeks visit including 8-weeks visit, interval after the 8-weeks visit including 16-weeks visit, interval after the 16-weeks visit including 24-weeks visit, interval after the 24-weeks visit including 36-weeks visit, and interval after the 36-weeks visit including 52-weeks visit.

Secondary endpoints are:

- Proportion of implanted subjects with treatment emergent adverse events. Treatment emergent adverse events are defined as events with onset during or after the implantation procedure.
- Proportion of implanted subjects with peristomal skin lesions will be evaluated using a validated 5-point scale by assessing signs of erythema, erosion, or papular lesions.
- Proportion of implanted subjects with device-related adverse event.
- Proportion of implanted subjects with device displacement, device revision or device replacement.

Photographs of the stoma are to be taken to document the ingrowth into the TIES® Port, surrounding peristomal skin and position of the implant at 4, 8, 16, 24, 36 and 52 weeks after implantation. At least 4 views are to be taken: horizontal, vertical frontal, vertical right and vertical left. Additional views may be required if skin lesions or device displacement develop.

The adverse events complicating end-ileostomy, continent ileostomy and pelvic pouch are well described in the literature. Adverse events known to complicate end-ileostomy include peristomal skin problems, infection, abscess, entero-cutaneous fistula, necrosis, stenosis, prolapse, retraction, parastomal hernia, incisional hernia, obstruction to emptying of intestinal contents. That said, the exact incidences are unknown because many reports are retrospective and the experience of the site may influence the outcomes.

All adverse events, device-related complications and device deficiencies or malfunctions described in section 4 will be fully summarized. Adverse events are to be assessed for seriousness and causality.

CLINICAL INVESTIGATION PLAN

For all definitions indicated in section 10.1, the total number of adverse events, percentage of subjects with at least one given adverse event (AE, ADE, SAE, SADE, USADE) will be reported in summary tables. Moreover, description of events will be presented in listings. Severity and relationship will be documented for all defined adverse events (AE, ADE, SAE, SADE, USADE).

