	
A Data Safety Monitoring Board will be appointed to review interim study results as discussed in section 9. A dermatologist will provide independent review of photographs of the stoma for peristomal skin lesions as required.

CLINICAL INVESTIGATION PLAN

Schedule of Assessments / Flow Chart:

Parameter/ Examination	Screening	Baseline ^a	Procedure (day 0)	Post OP (Daily follow up ^c)	Discharge	Visit 1 at 4 Weeks (+/- 7d)	Visit 2 at 8 weeks ^e (+/- 7d)	Visit 3 at 16 weeks (+/- 7d)	Visit 4 at 24 weeks (+/- 14 d)	Visit 5 at 36 weeks (+/- 14 d)	Visit 6 at 52 weeks (+/- 14 d)
Informed Consent		X									
Medical history	X	X									
Inclusion/Exclusion criteria	X	X									
Physical Examination ^f	X	X		X	X	X	X	X	X	X	X
Dipstick urine-analysis		X									
ECG		X									
Pregnancy test ^b		X									
Hematology and Chemistry		X									
Review and instruct on care of the stoma				X	X	X	X	X	X	X	X
Removal of Turnbull Adaptor ^d						X					
Start to use TIES® Lid							X				
Adverse Events (AE)			X	X	X	X	X	X	X	X	X
Safety evaluation			X	X	X	X	X	X	X	X	X
Concomitant medications		X	X	X	X	X	X	X	X	X	X
Ingrowth assessment						X	X	X	X	X	X
Photographs ^g of implant, stoma and adjacent skin			X		X	X	X	X	X	X	X
QOL questionnaires		X					X	X	X	X	X
Performance Questionnaire (Diary covering one 72-hours period)								X	X	X	X
Subject's preference questionnaire											X

^a The patient will be considered as enrolled only when the consent will have been signed. All the examinations performed before the enrolment are done according to routine practice at the hospital where the study takes place.

The baseline assessment should be performed not earlier than 12 weeks before the procedure.

^b Pregnancy test will be performed in woman of childbearing potential.

^c A follow up will be performed every day after the procedure prior to discharge from hospital.

^d Removal of Turnbull system will be performed at 4 weeks (+/- 7 days) only if it has not already detached by itself.

^eThe patient will continue to permanently use stoma bags until visit at 8 weeks for review of suitability to start using the TIES®Lid. If trimming of ileum is required, postpone use of TIES® Lid by about a week for healing.

^f Physical examination also includes weight measurement

^g At least 4 views of the stoma should be taken: horizontal, vertical frontal, vertical right and vertical left. Additional views may be required if skin lesions or device displacement develop.

CLINICAL INVESTIGATION PLAN

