8. ADVERSE EVENT MANAGEMENT

Subjects will be carefully monitored during the study for possible adverse events (AEs) from the time the subject signs the Patient Informed Consent form to the completion of their participation in the study. Any AE observed will be fully investigated by the Investigator and classified in line with the definitions of the ISO14155:2011 as described below.

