8.1. Definitions

Adverse Event (AE):

Any untoward medical occurrence, unintended disease or injury, or untoward clinical signs (including abnormal laboratory findings) in subjects, users or other persons, whether or not related to the investigational medical device

NOTE 1 This definition includes events related to the investigational medical device or the comparator.

NOTE 2 This definition includes events related to the procedures involved.

NOTE 3 For users or other persons, this definition is restricted to events related to investigational medical devices.

Treatment emergent adverse events are adverse events with onset at or following the implantation procedure for the purpose of this study.

Serious Adverse Event (SAE):

Adverse event that:

a) led to death,

b) led to a serious deterioration in the health of the subject, that either resulted in

- 1) a life-threatening illness or injury, or
- 2) a permanent impairment of a body structure or a body function, or
- 3) hospitalization or prolongation of existing hospitalization, or
- 4) medical or surgical intervention to prevent life-threatening illness or injury or permanent impairment to a body structure or a body function,

c) led to foetal distress, foetal death or a congenital abnormality or birth defect

NOTE Planned hospitalization for a pre-existing condition, or a procedure required by the Clinical Investigation Plan, without serious deterioration in health, is not considered a serious adverse event.

CLINICAL INVESTIGATION PLAN

Device Deficiency:

Inadequacy of an investigational medical device related to its identity, quality, durability, reliability, safety or performance. This may include malfunctions, use error, or inadequacy in the information supplied by the manufacturer.

Adverse Device Effect (ADE):

Adverse event related to the use of an investigational medical device

NOTE 1 This definition includes any adverse event resulting from insufficiencies or inadequacies in the instructions for use, the deployment, implantation, installation, operation, or any malfunction of the investigational medical device.

NOTE 2 This definition includes any event resulting from a use error or from intentional misuse of the investigational medical device.

Serious Adverse Device Effect (SADE):

Adverse device effect that has resulted in any of the consequences characteristic of a serious adverse event

Unanticipated Serious Adverse Device Effect (USADE):

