8.4. Investigator Reporting Responsibilities

The investigator should report to the sponsor the following events, whether expected or not, in the corresponding CRF form, with the exception of AEs / SAEs detected before the patients has signed the patient consent form.

- AE
- SAE
- Device Deficiencies that did not but might have led to a SAE if:
 - o Suitable action has not been taken or
 - o Intervention had not been made or
 - o If circumstances had been less fortunate
- New findings/updated in relation to already reported events

If an AE / SAE is present at the beginning of study prior to the subject providing signed consent to participate in the study, only its worsening should be reported.

The investigator will document all AEs on the Adverse Event Form, including (at a minimum) a description of the event, date of onset, severity, relationship to the investigational device and/or procedure, required interventions, duration, and outcome. The investigator will monitor all AEs until they are resolved, determined to be a chronic condition or the subject is lost to follow-up. The investigator will report all AEs regardless of whether it is anticipated or unanticipated and regardless of classification, seriousness, intensity, outcome or causality.

All Serious Adverse Events including all device deficiencies that could have led to a SAE should be reported to the Sponsor within 24 hours of awareness of an event via the Adverse Event electronic Case Report Form in the study's electronic database, as that will trigger an immediate e-notification to the Sponsor and Devicia. All device deficiencies should also be reported without unjustified delay.

If the e-CRF is unavailable, notification to the sponsor can be made by email and the email address is [contact]

CLINICAL INVESTIGATION PLAN

The investigator must ensure that all additional relevant information (i.e., radiology reports, hospitalization reports indicating the SAE) that becomes available is also forwarded to the sponsor immediately after the initial notification and the information should be de-identified.

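### The treatment-emergent definition tests onset only: an event that starts between consent and implantation and worsens afterwards is not counted, and the dating of a worsened pre-consent condition is left open

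*Combined protocol and SAP*

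**What the plan says.** The treatment-emergent rule appears in four places, always as a test of onset.

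- Section 10.7: "Treatment emergent adverse events are defined as events with onset during or after the implantation procedure". The Safety Evaluation in the synopsis and section 4.3 carry the same rule.
- Section 8.1: "Treatment emergent adverse events are adverse events with onset at or following the implantation procedure for the purpose of this study".

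None of the four mentions an event that began earlier and became worse.

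The collection and reporting rules cover a wider period.

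- Section 8 has subjects monitored for adverse events "from the time the subject signs the Patient Informed Consent form to the completion of their participation in the study".
- A footnote to the Schedule of Assessments adds: "The baseline assessment should be performed not earlier than 12 weeks before the procedure". The schedule places informed consent at the baseline visit.
- Section 8.4 says of an event already present "prior to the subject providing signed consent to participate in the study, only its worsening should be reported".
- Section 8.4 also lists, among the items that investigators must report, "New findings/updated in relation to already reported events".
- The adverse event form in 8.4 records a date of onset. No section says whether a worsening takes the date of the original condition or the date of the change.

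**The concern.** A treatment-emergent endpoint is meant to separate what arose or got worse after the intervention from what was there before. A rule based on onset alone captures new events and says nothing about deterioration. Here the collection period opens before surgery, so some reported events will already carry a pre-operative onset date when the Port is implanted.

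Deterioration of an existing condition is a plausible signal in this population. Section 5.1 admits patients who need an alternative to an existing ileostomy, continent ileostomy or pelvic pouch, and section 10.1 mentions patients who cannot tolerate stoma bags because of complications. The study has one arm, so no control group carries the same misclassification. If up to 25 sites date worsening in different ways, part of the between-site variation in the endpoint would reflect record-keeping.

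**Working it through.** The documents give no expected treatment-emergent rate, target or precision, so there is no figure of the plan's to reproduce. The check is to apply the stated rule to each type of event that the reporting rules can generate.

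| Type of event | Reported under 8.4 as | Onset date | Treatment-emergent as written? |
|---|---|---|---|
| A. Starts at or after implantation | New event | On or after surgery | Yes, as intended |
| B. Starts between consent and implantation, does not worsen | New event | Before surgery | No, as intended |
| C. Starts between consent and implantation, worsens afterwards | Update to a reported event | Before surgery | No, although the deterioration followed surgery |
| D1. Present before consent, worsens after implantation, dated at the worsening | The worsening is the event | After surgery | Yes |
| D2. As D1, but dated from the original condition | The worsening is the event | Before surgery | No |

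**Row C.** The event is already on record when it worsens. Section 8.4 calls for an update, and no rule gives the deterioration a new record or a new onset date. With the original onset retained, the event fails the test in all four definitions. If consent is signed at the baseline visit, the period in which such events can start is up to 12 weeks. The safety intervals in 10.7 begin with hospitalisation, so an event that started before admission has no interval of its own either.

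**Rows D1 and D2.** These are the same clinical event under two dating conventions. Because 8.4 makes the worsening the reportable item, D1 is the more natural reading. The text does not rule out D2.

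**Scale.** Suppose k implanted subjects have an uncounted worsening and no other treatment-emergent event, and N subjects are implanted. The proportion is then too low by k/N. Taking N = 200, the planned minimum enrolment, as the number implanted (an assumption):

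- k = 1: 1/200 = 0.5 percentage points
- k = 4: 4/200 = 2 points
- k = 10: 10/200 = 5 points

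These values only show the scale. The documents contain nothing from which k could be estimated. A subject with any other treatment-emergent event in the follow-up year is already counted and adds nothing to k.

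**The case against.** The strongest reply has four parts.

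1. **Conditions present before consent.** A baseline condition is medical history, not an adverse event. The reported event is its worsening, which naturally takes a post-operative onset and meets the definition. This stands as the better reading. A reader might infer that every pre-existing condition that deteriorates is excluded from the endpoint. The documents do not support that, because they leave the dating open.

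2. **Other outputs show these events.** Section 10.7 summarises all adverse events by subject and in listings. It also has separate endpoints for device-related events and for peristomal skin lesions, neither limited by onset. This largely stands, so a reader should not conclude that the safety signal disappears. These outputs do not replace the endpoint, however. The all-event tables mix pre-operative with post-operative events, the device-related endpoint depends on attribution, and the skin endpoint covers skin only.

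3. **The effect cannot be sized from the skin figures.** It is tempting to apply the rate of at least 30% for skin problems (sections 1.1 and 10.4) to subjects entering with a stoma. That would describe mainly the pre-consent group, where exclusion is not established, and a condition that has its own endpoint. It would also ignore subjects counted through another event. The share of subjects entering with a stoma and the share who worsen are not in the documents. This part stands in full.

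4. **Derivations are left to a later analysis plan (section 10.9).** This stands in part. That plan can add worsening to the definition, but it cannot recover a date of worsening that sites were never told to record.

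**Conclusion.** The point holds in a limited form. For events that start between consent and implantation and worsen afterwards, the written rule gives the wrong classification. This rests on the literal wording of the four definitions and on 8.4 treating later changes as updates. For conditions present before consent, the defect is a missing dating rule that may be applied differently across sites.

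The effect on the endpoint cannot be derived from the documents and is probably small. It requires a pre-operative onset, a post-operative worsening and no other treatment-emergent event in the same subject. The endpoint is secondary and descriptive, and the safety analysis in 10.7 sets no test or threshold on it. The correction is worth making because it is simple and because the dating rule has to be in place while data are being collected.

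**What to change.** - In the synopsis (Safety Evaluation) and in sections 4.3, 8.1 and 10.7, define treatment-emergent as: *onset, or worsening in severity or seriousness, during or after the implantation procedure*. The severity grades in 8.2 can serve to identify a worsening in severity.
- In section 8.4, state that a worsening is entered as its own event with the date of worsening as its onset. Apply this both to conditions present before consent and to events first reported between consent and implantation.
- Carry the same definition into the statistical analysis plan announced in section 10.9.

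The cost is one sentence in each place and an eCRF completion note, with no change to visits or procedures. The downside is that the reported treatment-emergent rate may be slightly higher.
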